- 3. Arrhythmic myocarditis is largely underdiagnosed and uninvestigated. Importantly, myocarditis presenting with arrhythmias requires specific diagnostic, prognostic and therapeutic considerations [2]. At our hospital, which is an international referral center for ventricular arrhythmias management and ablation, a relevant number of patients with unexplained arrhythmias had myocarditis as underlying aetiology. Our experience may considerably improve knowledge and management of arrhythmic myocarditis.
- 4. The role of CMR, as well as alternative nonivasive imaging techniques, in defining myocarditis healing is a relevant issue. In particular, optimal timing for follow-up diagnostic reassessment is still to be defined, in patients with myocarditis at different inflammatory stages, either with or without aetiology-dependent treatment [4,7].
- 5. Uniformly-designed studies are lacking, to compare myocarditis among different patient subgroups, differing by variables like: clinical presentations, myocarditis stage, associated cardiac or extra-cardiac diseases, aetiology-based treatment, associated arrhythmic manifestations, diagnostic workup, and devices or ablation treatment [8,9,10].

AIMS

Our study has multiple aims (full detail in Table 1).

- 1. To compare EMB with nonivasive diagnostic techniques (CMR, DECT, PET scan, either alone or in association).
- 2. To assess the role of blood biomarkers for identification of aetiology, predisposition, prognosis, response to treatment, inflammatory activity, clinical presentation.
- 3. To describe myocarditis presenting with arrhythmias, with special focus on ventricular arrhythmias at different myocarditis stages and in different clinical contexts. To validate and generalize our model for optimal diagnostic and therapeutical management of arrhythmias in myocarditis patients (given the role of our hospital as an international referral center for arrhythmias ablation and management).

- 4. To evaluate the timing needed for myocarditis healing in different patients subgroups, as assessed by nonivasive imaging techniques (CMR, DECT, PET scan), either alone or in association.
- 5. To compare patients subgroups of myocarditis, in terms of epidemiology, aetiology, prognosis, and diagnostic-therapeutical strategies. Among the others, the main study subgroups will be:
 - A. Arrhythmic vs. non-arrhythmic myocarditis.
 - B. Arrhythmic myocarditis subgroups.

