 - C. Non-arrhythmic myocarditis subrgoups (i.e.: fulminant, acute coronary syndrome-like, pericarditis-like, heart failure, nonischaemic dilated /hypokynetic cardiomyopathies of unknown aetiology...).
 - D. Infectious vs. aoutoimmune vs. toxic myocarditis.
 - E. Myocarditis treated by aetiology-based treatment vs. isolated cardiac medical treatment.
 - F. Myocarditis at different disease stages: acute, hyperacute, fulminant, chronic active, post-inflammatory, or active vs. previous vs. non-myocarditis.
 - G. Myocarditis presenting as organ-specific diseases vs. in the context of a genetic disorder or systemic disease.
 - H. Myocardits vs. peri-myocarditis/myo-pericarditis.
 - I. Other analyses.

STUDY DESIGN

Our study, previously designed as a single-center experience, is multicenter, observational and both retrospective and prospective.

Retrospective phase includes all clinical data occurring before the index event (hospitalization or clinically suspected myocarditis) and myocarditis diagnosis. Prospective phase includes all data following index event and myocarditis diagnosis.

Any adult patient with clinically suspected myocarditis, of any clinical presentation and any degree of severity, will be considered as suitable for study enrollment.

Patients will undergo diagnostic and therapeutical strategies considered as clinically indicated in a patient-tailored manner, as suggested by international guidelines recommendations and best local clinical practice. Patients will be free of either accepting or refusing any diagnostic or therapeutical proposal. Whenever accepted, data will be simply collected and analyzed.

Based on clinical presentation, patients will be divided into two groups, arrhthmic (group A) and non-arrhythmic (group NA, including any other clinical presentation).

Independently of A/NA groups, all patients will undergo optimal diagnostic and therapeutic strategies, as summarized in panel A. In parallel, special diagnostic and therapeutical strategies will be performed in patients with arrhythmic presentation or evidence of arrhythmias, as shown in panel B. Proposed flowcharts (panels A and B) represent only an approximate algorithm. Exceptions can be made in single cases, based on clinical indications.

Panel A – Diagnostic and therapeutical workup in all patients.

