Independently of groups (A/NA), all patients will undergo optimal diagnostic and therapeutical workup, guided by updated scientific evidence merged with the clinical experience of the center.

Baseline diagnostic workup will include: complete blood exams, 12-leads ECG, continuous telemetric monitoring, transthoracic doppler echocardiogram, coronary artery imaging (coronary angiography or CT scan). Any other clinically relevant diagnostic test will be collected.

In life-threatening presentations (cardiogenic shock or malignant arrhythmias), support treatment by optimal medical therapy, inotropic or mechanical circulatory support, and acute-phase arrhythmia management (including cardioversion, defibrillation, or temporary pacing) will be performed, as indicated, before completing diagnostic workup. Final diagnosis of myocarditis will include, whenever applicable:

- A. For stable patients: 1) a second-level imaging technique (CMR as first choice; and/or DECT, PET, or multiple/fusion imaging techniques, based on clinical indications); followed by: 2) EMB, whenever clinically indicated. Blood exams for aetiology screening will be personalized upon clinical indications.
- B. For unstable patients: EMB only, as recommended. Blood exams for aetiology screening will be personalized upon clinical indications.

Diagnostic criteria for myocarditis, as assessed by any diagnostic technique, will be defined based on international scientific evidence and will be constantly updated. Similar considerations apply to myocarditis staging and aetiology definition. Whenever not available at local institutions, diagnostic exams can be performed and analyzed at external centers.

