- Intensive FU: cardiological (or multidiciplinary) assessment 1-2/y with blood exams (at least troponin, natriuretic peptides, and inflammatory indexes), 12-leads ECG, Holter

ECG monitoring, device interrogation (in device carriers), and color Doppler transthoracic echocardiogram. Minimal reassessment timespan is 2 weeks. At least one second-level imaging techniques (CMR, DECT, PET scan) will be performed by 12 months (approximately at 3, 6, 9, or 12 months based on clinical indications). Exercise stress test will be performed whenever clinically indicated, usually not before proved myocarditis healing. Other exams will be performed based on clinical indications.

STUDY DURATION

Estimated study duration is 23 years (from Jaunary 2013 to December 2035). In detail:

- Retrospective enrollment: from January 2013 to local institute review board approval.
- Prospective enrollment: from local institute review board approval to Dicember 2025 (estimated enrollment end).
- FU duration per patient: 10 years.
- Estimated last FU for last enrolled patient: December 2035.

CONFOUNDING FACTORS

Not applicable.

EPIDEMIOLOGIC DATA

Because of multiple clinical presentations and heterogeneous diagnostic techniques, myocarditis incidence is widely variable [1].

At our institution, the mean rate of clinically suspected myocarditis is not inferior to 4 new cases/month. Epidemiology may be different at other centers.

Target numbers reported in Table 1 are reasonable.

DATA COLLECTION AND STATISTICAL ANALYSIS

Two enrollment modalities are accepted for this study: 1) prospective enrollment: at myocarditis diagnosis (following local institute review board approval); 2) retrospective enrollment: during FU of myocarditis patients (diagnosed before local institute review board approval).

Considering incidence rate, local and general epidemiology, enrollment of 1000 myocarditis cases by December 20205 is expected, including retrospective and prospective enrollment. For aim 1, 95% confidence intervals of 81-89% and of 75-85% are estimated for EMB and CMR, with 85% and 80% sensitivity, respectively. These data are consistent with updated knowledge. EMB will be considered as the diagnostic gold standard, as indicated [1].

Both baseline and FU data will be collected for each enrolled patient. CRF form reports the main study variables, in the form of an Excel document.

Statistical analyses will be performed by certified programs (i.e. SPSS).

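### Aim 1's imaging–EMB pairs come from a predominantly stable, selectively biopsied subset of the 1000 patients in Table 1, so unadjusted CMR accuracy may be biased in a direction the protocol does not fix

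*Protocol*

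**What the plan says.** - **Aim.** Aim 1 (Protocol, Aims) is "To compare EMB with nonivasive diagnostic techniques (CMR, DECT, PET scan, either alone or in association"). Table 1 gives this aim 1000 patients, with diagnostic concordance as the primary variable and diagnostic accuracy among the secondary ones.
- **Reference test.** In Data Collection and Statistical Analysis, "EMB will be considered as the diagnostic gold standard, as indicated". The same section expects 1000 cases in all and projects sensitivities of 85% for EMB (95% CI 81–89%) and 80% for CMR (75–85%).
- **Stable patients** (Study Design, Panel A). Imaging comes first: "For stable patients: 1) a second-level imaging technique (CMR as first choice" and alternatives), "followed by: 2) EMB, whenever clinically indicated".
- **Unstable patients** (same place). "For unstable patients: EMB only, as recommended".
- **Further selection** (Study Design). "Patients will be free of either accepting or refusing any diagnostic or therapeutical proposal". The flowcharts "represent only an approximate algorithm. Exceptions can be made in single cases, based on clinical indications".

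The protocol does not define a set of patients with both tests, give the share expected to have both, or mention selective biopsy. The section on confounding factors is marked as not applying.

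**The concern.** The reference test is ordered after the index test, on clinical grounds, with the imaging result already known. This is partial verification. If patients with positive imaging are biopsied more often, myocarditis missed by imaging also tends to go unbiopsied: apparent sensitivity rises and apparent specificity falls. If biopsy is used mainly to settle cases that imaging left negative or unclear, the opposite happens.

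The protocol makes some dependence plausible. In Panel A, new imaging abnormalities are one trigger for reassessment, which may include EMB, and aetiology-dependent treatment is reserved for active, biopsy-proven disease. It also gives reasons to biopsy unclear cases, such as unexplained arrhythmias and differential diagnosis.

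At stake are the projected CMR sensitivity, the concordance figure computed in the same pairs, and how far either extends. Enrolment covers every degree of severity, but the default pathway gives unstable patients no baseline imaging to pair with the biopsy.

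**Working it through.** **1. The plan's own figures.** A Wald interval is p ± 1.96·√(p(1−p)/n). At n = 1000:
- EMB, p = 0.85: 82.8–87.2%
- CMR, p = 0.80: 77.5–82.5%

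The stated intervals are wider. Inverting, n = 1.96²·p(1−p)/h²:
- EMB, h = 0.04: n ≈ 306 (242–400 allowing for rounding)
- CMR, h = 0.05: n ≈ 246 (203–304)

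A common denominator of about 242–303 reproduces both. The stated precision thus matches roughly a quarter to 30% of 1000 patients. The protocol does not name that denominator or say how those patients would be selected.

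**2. Apparent accuracy under selective biopsy.** Let v1 and v0 be the EMB rates after positive and negative CMR, let biopsy depend only on the CMR result, and let r = v1/v0. Then

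- apparent Se = Se·r / (Se·r + (1−Se))
- apparent Sp = Sp / (Sp + (1−Sp)·r)

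Inputs: Se = 0.80 (protocol). Sp = 0.80 and every r are assumptions, since the protocol gives no specificity and no biopsy rate by imaging result.

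| r | Apparent Se | Apparent Sp |
|---|---|---|
| 0.5 | 0.40/0.60 = 66.7% | 0.80/0.90 = 88.9% |
| 1 | 0.80/1.00 = 80.0% | 0.80/1.00 = 80.0% |
| 1.5 | 1.20/1.40 = 85.7% | 0.80/1.10 = 72.7% |
| 2 | 1.60/1.80 = 88.9% | 0.80/1.20 = 66.7% |
| 3 | 2.40/2.60 = 92.3% | 0.80/1.40 = 57.1% |

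Only the ratio matters, and apparent sensitivity does not depend on the assumed specificity. At r = 2, apparent specificity is 53.8% if the true value is 70%, and 81.8% if it is 90%.

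**3. Ratio at which the stated upper limit is passed.** Apparent Se = 0.85 requires 0.80·r/0.20 = 0.85/0.15, so r = 5.667/4 ≈ 1.42.

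**4. Raw concordance, the primary variable.** With Se = Sp = 0.80, r = 2 and prevalence π,

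agreement = (1.6π + 0.8(1−π)) / (1.8π + 1.2(1−π)).

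- π = 0.3: 1.04/1.38 = 75.4%
- π = 0.5: 1.20/1.50 = 80.0%
- π = 0.7: 1.36/1.62 = 84.0%

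Without selection it is 80% at every prevalence. The shift is 0 to about 5 points, in either direction.

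**The case against.** **Bias is possible, not shown.** A reader might infer that CMR accuracy in this study is biased, and biased upward. The documents do not support that. No passage says that EMB depends on the imaging result, and no EMB rate is given. Equal rates would leave sensitivity and specificity unbiased among stable patients, and r = 0.5 lowers apparent sensitivity to 67%. This objection stands, so the claim is conditional.

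**Stable-only is too strong.** A reader might also infer that unstable patients can contribute no pairs. Panel A is approximate and allows exceptions, reassessment may include imaging and EMB, and patients with active myocarditis have at least one second-level imaging test by 12 months. Late imaging is a poor partner for a baseline biopsy, but the accurate term is predominantly stable.

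**The 1000 is a count of patients, not of pairs.** Correct. Aim 1 also holds analyses that need no biopsy, such as CMR or DECT against PET. What remains is that the number of pairs is stated nowhere and the default pathway would not be expected to yield 1000.

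**Concordance, not accuracy, is primary.** Also correct, and its shift is smaller. Accuracy is still a listed variable, and sensitivity is the only quantity the protocol projects for this aim.

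**The correction belongs in the statistical analysis plan.** Partly. The choice of model can wait for that document, which is not at hand. Which patients the aim concerns, what must be recorded, and how far the claim reaches belong in the protocol, because unrecorded reasons for biopsy cannot reliably be recovered later.

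**Conclusion.** The concern holds in conditional form. The default pathway yields imaging–EMB pairs from a selectively biopsied, predominantly stable subset, and nothing in the protocol offsets this. Whether unadjusted accuracy is biased, and which way, depends on biopsy rates that the protocol does not give. Over assumed ratios of 0.5 to 3, apparent CMR sensitivity runs from 67% to 92% around a true 80%, so a modest preference for biopsying CMR-positive patients (a ratio above about 1.42) would put it above the protocol's range with no change in the test. The specificity and concordance figures rest further on assumed specificity and prevalence. These are illustrations of exposure, not predictions. The point should be fixed, but it does not invalidate the aim.

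**What to change.** In Table 1 (aim 1) and in Data Collection and Statistical Analysis, for the accuracy and concordance analyses:

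1. Define the population as enrolled suspected cases with baseline second-level imaging, whether or not biopsied.
2. Record the reason for performing or not performing EMB, and report EMB rates by imaging result and by stability.
3. Give Begg-Greenes or inverse-probability-of-biopsy-weighted estimates beside the naive ones, using recorded baseline predictors. The CRF is not shown, so their availability must be confirmed. Add a sensitivity analysis for unrecorded reasons for biopsy.
4. Report any pairs from unstable patients separately, and limit conclusions to predominantly stable patients.
5. State the expected number of imaging–EMB pairs beside the 1000.

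**Cost.** Wording, a small recording burden and one additional model, with no extra biopsies and no change to care. Intervals will be wider and the claim narrower.

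**Limits.** The correction works only if imaging-negative, unbiopsied suspected cases stay in the dataset. The inclusion criteria admit suspected cases, but the analysis section describes enrolment at diagnosis or during follow-up of myocarditis patients, so this needs to be made explicit. The correction also does not address EMB sampling error, which the protocol's Rationale acknowledges.

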All patients with myocarditis (or any alternative final diagnosis), will undergo standard cardiological optimal medical treatment (COMT), as indicated. By converse, aetiology-dependent treatment will be performed only in patients with a final diagnosis of any *active* (acute, fulminant, chronic active) myocarditis of defined aetiology (EMB-proved). Multidisciplinary assessment, including infective disease specialists (in viral/infective myocarditis), immunologists (in non-infective/autoimmune myocarditis) or any other specialist as needed, will be used to identify indications to treatment, drug choice (either approved or with a justified off-lable indication), treatment duration and safety profile, aiming at the best patients' interest. Toxic myocarditis will be treated accordingly, by evaluating the opportunity of withdrawing pathogenic noxa.

This protocol will not interfere with local best clinical practice.

Patients with *non-active* myocarditis (previous or healed) or with non-myocarditis, will undergo "standard FU" (see below). Patients with *active* myocarditis will undergo "intensive FU" (see below).

Independently of FU modalities, diagnostic reassessment will be considered in the presence of at least one of the following *instability* criteria: a) new unexplained cardiac symptoms (dypnoea, chest pain, syncope, palpitation); b) new unexplained increase in troponin or natriuretic peptides; c) new imaging abnormal signs; d) new unexplained clinically relevant arrhythmias. Diagnostic reassessment will include second-level imaging and/or EMB, as shown above. Subsequent therapeutical workup will be in line with the above explanations. In stable patients or undergone myocarditis healing, exercise stress test will be obtained, whenever possible.

Panel B - Diagnostic and therapeutical workup of patients with arrhythmias

In parallel with (and independently of) Panel A content, patients with arrhythmias (group A) will undergo specific diagnostic and therapeutical management for arrhythmias, as a result of the integration between international guidelines recommendations and the experience of a third-level center international referral center (San Raffaele Hospital, Milan) for arrhythmia management and ablation.

To oversimplify, 4 groups of patients will be considered.

1. Group 1: major ventricular arrhythmias (haemodynamically unstable VT, hu-VT; ventricular fibrillation, VF).

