After electrical stabilization and support treatment (panel A), indication to secondary prevention ICD implant will be multiparametric and patient-tailored. In patients with active myocarditis, subcutaneous ICD (S-ICD) or wearable CD (WCD) will be considered. Antiarrhythmic drugs will be considered in all Group 1 patients. In addition, all Group 1 patients will undergo COMT and aetiology-dependent treatment whenever applicable (panel A). Ablation of ventricular arrhythmias will be considered in patients with severe arrhythmic presentation, or symptomatic, or refractory to optimal medical treatment. Electrophysiological study (EPS) may be used in selected cases. A CRT-D will replace ICD whenever indicated.

2. Group 2: other ventricular arrhythmias (high-burden premature ventricular complexes = hb-PVC; nonsustained VT = NSVT; haemodynamically stable VT = hs-VT). Whenever clinically indicated, Group 2 patients will undergo invasive EPS (or in alternative nonivasive programmed ventricular stimulation in ICD carriers) to stratify arrhythmic risk. Patients with positive EPS will undergo ICD (or S-ICD/WCD) as in Group 1. Patients with negative EPS, as well as Group 2 cases not undergoing EPS, will undergo watchful waiting strategy (always with an intensive FU) with or without loop recorder implant: in these cases, ICD (or S-ICD/WCD) will be implanted only following documentation of relevant VA in FU. In addition, all Group 2 patients will undergo antiarrhythmic treatment, COMT and aetiology-dependent treatment whenever applicable (panel A). In symptomatic or drug-refractory cases, ablation of ventricular arrhythmias will be considered. A CRT-D will replace ICD whenever indicated.

3. Group 3: bradyarrhythmias (2nd type II or 3rd degree atrioventricular block = advanced AVB; critical sinus pauses = SND).

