- Age \geq 18 years.

- Clinically suspected myocarditis [1].
- Enrollment performed by one of the participating Centers.

EXCLUSION CRITERIA

- Absence of written informed consent.
- Age < 18 years (paediatric population).

VARIABLES AND ENDPOINTS

The main study variables are reported in Table 1 and in CRF. Endpoints will include:

- Major endpoints: death; cardiac death; malignant ventricular arrhythmias (= VT, VF, appropriate ICD therapy); heart transplantation; end-stage heart failure.
- Minor endpoints: minor arrhythmias (NSVT; supraventricular arrhythmias; bradyarrhythmias); structural or functional myocardial abnormalities (any chamber dilation, systolic or diastolic dysfunction, including strain analysis, pericardial, vascular or valvular involvement, any other detectable abnormalities); abnormalities detectable by advanced imaging techniques (Lake Louise criteria and T-mapping techniques at CMR; any qualitative or quantitative imaging abnormality detectable by CMR, DECT or PET scan, or other imaging techniques, alone or in association); clinical variables (signs and symptoms related to cardiac or multisystemic disease; identification of associated diseases); blood exams abnormalities (inflammatory indexes; cardiac injury, inflammation or stress biomarkers; cardiac and extracardiac autoantibodies; genetic tests; tissue/organ damage indexes; markers of treatment toxicity; others); anatomical or functional abnormalities of coronary macro or microvascular structures (coronary angiography; CT scan; histology; provocative stress tests, nuclear medicine techniques); necessity of invasive elctrophysiological techniques (electrophysiological study; arrhythmia ablation; device implant) and related findings; indications and timing for primary and secondary prevention device implant, in relation with different therapeutic strategies; myocarditis recurrences; response to general and specific treatement; multiparametric modeling of prognostic risk stratification and response to treatment prediction; elaboration of multidisciplinary workup models.

The main pimary and secondary variables are reported in detail in Table 1.

Tabella 1

N	Aim	N patients	Primary Variables	Secondary variables

MYOCAR - Version V03 - Multicenter

Principal Investigators: [name] - [name]

1 Comparison between EMB 1000 Diagnostic Inflammation 	ory activity (presence; type;
and second level imaging concordance quantificat	
findings • Fibrosis (p	resence; type; quantification)

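### In Group 2 the EPS result decides who carries an ICD at the start, and the malignant-arrhythmia endpoint is partly defined by, and better detected with, that ICD

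*Protocol*

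**What the plan says.** - **Endpoint.** Variables and endpoints lists five major endpoints. One of them is "malignant ventricular arrhythmias (= VT, VF, appropriate ICD therapy". The others are death, cardiac death, transplantation and end-stage heart failure.
- **Device rule by EPS.** Panel B, Group 2, uses EPS where clinically indicated "to stratify arrhythmic risk". It then states: "Patients with positive EPS will undergo ICD (or S-ICD/WCD) as in Group 1". For EPS-negative patients and those not tested it states: "in these cases, ICD (or S-ICD/WCD) will be implanted only following documentation of relevant VA in FU". A loop recorder is optional for them.
- **Device rule by group.** The ICD rules sit in Panel B, under which "patients with arrhythmias (group A) will undergo specific diagnostic and therapeutical management for arrhythmias". They are not uniform. For Group 1, "indication to secondary prevention ICD implant will be multiparametric and patient-tailored". Group 3 may have watchful waiting, a pacemaker or an ICD. Group 4 has no ICD rule.
- **Surveillance.** Under Follow-up variables, continuous monitoring is foreseen during a new hospital stay or where a device is carried. Under Follow-up exams, interrogation applies to carriers. All patients have ECG and Holter at visits.
- **Use of the endpoint.** Table 1 makes differences on the major outcomes the primary variable for aim 5, whose first contrast is "Arrhythmic vs. non-arrhythmic myocarditis". Under aim 3 it lists, among secondary variables, the role of EPS in risk stratification and the search for device-implant criteria.
- **Handling.** Confounding factors is answered as not applicable. The statistical section names regression and survival models in general terms and says nothing about device status.

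**The concern.** A prognostic comparison needs the outcome to be sought equally at each level of the predictor. In Group 2 it is not. The EPS result sets device status at the start of follow-up, and the device then both supplies one component of the endpoint and improves detection of another. A VT that ends by itself or passes without symptoms is recorded in a carrier. In a non-carrier it is recorded only if it falls within a Holter, an ECG or an optional loop recorder. EPS could then look prognostic partly because a positive result installs the detector, and device criteria would be judged partly on an event that requires the device. These results are meant to inform how arrhythmic myocarditis is managed, so the direction of the error matters: it favours the test and the device criteria.

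**Working it through.** The protocol states no event rate, ICD coverage, detection rate or power for aims 3 or 5, so it has no figure to reproduce. Its one precision statement (sensitivity of biopsy and CMR, aim 1) does not bear on this point.

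**Step 1: the gap in surveillance.** Follow-up timeline sets six intensive visits in the first 24 months (3, 6, 9, 12, 18, 24). Suppose one 24-hour Holter at each, which is the minimum duration the protocol names. Recorded time is then 6 / 730 days = 0.8% of follow-up. This is not a capture rate, because symptomatic episodes come to notice in other ways. It shows that silent VT in a non-carrier can easily be missed.

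**Step 2: apparent risk ratio with no true difference.** Let *c* be the share of a group with an ICD and *d* the share of VT/VF captured without one, with capture taken as complete in carriers. For a true risk *R*:

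observed risk = *R* × [*c* + (1 − *c*) × *d*]

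*R* cancels in the ratio. The values of *c* and *d* are assumptions, and *c* is held fixed over follow-up for simplicity.

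Example, EPS-positive *c* = 1.0, EPS-negative *c* = 0.1, *d* = 0.5: 1.00 / (0.1 + 0.9 × 0.5) = 1.00 / 0.55 = 1.82.

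| Comparison (assumed ICD coverage) | d = 0.5 | d = 0.7 | d = 0.9 |
|---|---|---|---|
| EPS+ vs EPS− (100% vs 10%) | 1.82 | 1.37 | 1.10 |
| EPS+ vs EPS− (90% vs 20%) | 1.58 | 1.28 | 1.08 |
| A vs NA (50% vs 5%) | 1.43 | 1.19 | 1.05 |
| A vs NA (40% vs 10%) | 1.27 | 1.12 | 1.03 |
| A vs NA (30% vs 10%) | 1.18 | 1.08 | 1.02 |

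With equal capture (*d* = 1) every ratio is 1.00.

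**Step 3: chance of a false significant result.** Assume *R* = 20%, two-sided alpha 0.05 (the protocol gives 0.05 without sidedness) and 250 per group. The 250 is an even split of aim 5's target of 500; the protocol gives no split and no EPS numbers. The normal approximation is

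Φ[(p1 − p2 − 1.96 × SE0) / SE1],

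with SE0 pooled and SE1 unpooled. For EPS at *d* = 0.7, p1 = 0.200 and p2 = 0.146, so SE0 = 0.0338 and SE1 = 0.0337. This gives Φ[(0.054 − 0.0663) / 0.0337] = Φ(−0.365) = 36%.

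| Comparison | d = 0.5 | d = 0.7 | d = 0.9 | nominal, this direction |
|---|---|---|---|---|
| EPS+ vs EPS− (100% vs 10%) | 80% | 36% | 7% | 2.5% |
| A vs NA (40% vs 10%) | 17% | 8% | 4% | 2.5% |

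Smaller groups, which are likely for EPS, lower these chances but leave the ratios in Step 2 unchanged.

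**Step 4: device status as a covariate.** In EPS-positive patients the device follows from the predictor. In EPS-negative or untested patients, "ICD (or S-ICD/WCD) will be implanted only following documentation of relevant VA in FU", so it follows from an event that may itself meet the endpoint. Adjusting for device status would therefore condition partly on the predictor and partly on the outcome.

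**The case against.** Several objections have force.

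- **The endpoint is not closed to non-carriers.** A reader might infer that only ICD carriers can reach it. The documents do not support that. VT and VF count in anyone, ICD therapy is one of three alternatives inside one of five listed endpoints, and the other four need no device. The problem is unequal detection, not exclusion.
- **Group A is not uniformly under continuous monitoring.** A reader might infer this from Panel B and carry the EPS argument over to aim 5A in full. But the Group 1 ICD decision is individualised, Group 2 patients without a positive EPS start without an ICD, Group 3 may have none, and Group 4 has no ICD rule. The protocol also recognises primary-prevention ICDs for severe systolic dysfunction, so non-arrhythmic patients may carry them, and it calls its flowcharts approximate. A ratio such as 1 / 0.5 = 2.0 needs 100% against 0% coverage, which no rule in the protocol produces for A vs NA.
- **Non-carriers are followed.** Holter is part of both follow-up schedules, EPS-negative and untested Group 2 patients always have intensive follow-up, and some have loop recorders. This narrows the gap but does not close it.
- **A statistical analysis plan may deal with it.** Component displays and model details belong there, and their absence is not the complaint. But the protocol itself fixes the endpoint and the EPS-driven device rule, and then declares confounding not applicable.
- **No endpoint is device-neutral.** An ICD may abort an arrest, which biases a clinical endpoint the other way. This stands, and is a reason to report both definitions.

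**Conclusion.** The point holds for the aim 3 analyses of EPS and device criteria, and in weaker form for aim 5A. With no true difference, the apparent risk ratio is about 1.1–1.8 for EPS-positive vs EPS-negative and about 1.0–1.4 for A vs NA. This assumes 50–90% capture without a device, complete capture with one, and ICD coverage of 90–100% vs 10–20% (EPS) and 30–50% vs 5–10% (A vs NA). None of these inputs is in the documents, so the size is illustrative. The direction follows from the protocol's own rules whenever capture without a device is incomplete. At the favourable end, 90% capture, the effect on A vs NA is negligible. It would be wrong to conclude that any observed EPS or group effect is an artefact: the protocol's definition cannot separate a true effect from one of detection.

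**What to change.** 1. For the EPS and device-criteria analyses, and as a sensitivity analysis for A vs NA, add an arrhythmic endpoint that does not count events known only from device therapy or device interrogation. An example is cardiac death, cardiac arrest or VF, or sustained VT that is clinically manifest or recorded on surface ECG.
2. Report it beside the current definition. Always show the ICD-therapy component separately, and describe device status and implant date by group.
3. Replace the not-applicable entry under Confounding factors with a statement of this ascertainment bias. Add that no endpoint is fully device-neutral, because ICDs may also abort arrests.
4. Do not rely on a time-dependent device covariate as the remedy, for the reason in Step 4 of the working.

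The cost is one further endpoint definition and a parallel analysis, with fewer events and wider intervals for the new endpoint. It also needs the source of each arrhythmia record and the implant date. The CRF is not shown, so whether these are already collected cannot be checked. No change to device indications is implied.
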